**NCT number: NCT02380573**

**IRB Approval Date: 11-06-2015**

**Unique Protocol ID: HSC20150410H**

## Protocol Template Form

|                                |  |
|--------------------------------|--|
| Item 1 UTHSCSA Tracking Number | Cognitive and Functional Connectivity Effects of Methylene Blue in Healthy Aging, Mild Cognitive Impairment and Alzheimer's Disease |
|--------------------------------|--|

|  |  |
|--|--|
| Item 2 Abstract / Project Summary | Provide a succinct and accurate description of the proposed research. State the purpose/aims. Describe concisely the research design and methods for achieving the stated goals. This section should be understandable to all members of the IRB, scientific and non-scientific.
DO NOT EXCEED THE SPACE PROVIDED. |
|--|--|

**Purpose/Objectives:** The purpose of the current proposal is to test the hypothesis whether daily oral MB for two week period (and up to 12 weeks if subject decides to continue participation) will improve memory, attention, cognition and functional connectivity in healthy aging volunteers, mild cognitive impairment (MCI) and Alzheimer's disease (AD) subjects by using objective MRI readouts and standard neuropsychological tests.

**Research Design/Plan:** Adult volunteers will be studied using a randomized, double-blinded, placebo-controlled design. MB and Placebo arms will be included for healthy aging, MCI and AD groups. MB and placebo pills will be compounded into blue immediate release capsules. Each arm will also receive a pill of Azo (phenazopyridine hydrochloride) with each daily dose as urinary tract analgesic and to maintain coloration of the urine in both groups. Subjects will have MRI scanning on two different days, fourteen days apart. After visit #2 is completed, the subject will be given the option to continue the study for another 10 weeks.

**Methods:** This study will use a low-dose oral USP MB (282mg) daily over a two-week period and subjects will take drug daily for two weeks combined with an additional daily dose of 97.5mg of Azo. Subjects will take 3 pills of MB/placebo each day (1 with each meal (94mg of MB per pill) and 1 pill of Azo for 14 days.

Daily dose intake may be extended to 12 weeks after the initial follow up visit.

**Clinical Relevance:** Middle-aged and elderly people with MCI are at high risk for developing Alzheimer's disease, a condition that slowly destroys memory and thinking skills. Approximately 5.2 million Americans are living with AD today and this number is predicted to triple by 2050. There is a critical need for therapies that can arrest the progression from MCI to AD and other dementias, and for objective and sensitive measures of efficacy for interventions.

|                             |  |
|-----------------------------|--|
| Item 3
Background | 
Middle-aged and elderly people with mild cognitive impairment (MCI) are at high risk for developing Alzheimer's disease (AD), a condition that slowly destroys memory and thinking skills. Approximately 5.2 million Americans are living with AD today and this number is predicted to triple by 2050^1. There is a critical need for therapies that can arrest the progression from MCI to AD and other dementias, and for objective and sensitive measures of efficacy for interventions.
 
USP methylene blue (MB) is a FDA-grandfathered drug safely used to treat methemoglobinemia, carbon dioxide and cyanide poisoning in humans. Daily 4 mg/kg oral MB has been used safely for one year in clinical trials. Oral MB readily enters the brain and has unique energy-enhancing and antioxidant properties and acts in the mitochondria to sustain or enhance ATP energy production, thereby promoting neuronal cell survival and cognitive enhancement. MB has recently been shown to reduce behavioral impairments in animal models of Parkinson's disease and Alzheimer's disease. Our laboratory has shown with magnetic resonance imaging (MRI) that low-dose MB (intravenous 1 mg/kg) increases glucose uptake, oxygen consumption, blood flow and evoked responses in the rat brain in vivo. We also found that MB treatment reduces MRI-defined lesion and behavioral deficits in animal models of traumatic brain injury and stroke.
 
As the first step to translate these experimental findings to humans, we are carrying out a
 |
|-----------------------------|--|

|  |  |
|--|--|
|  | 
randomized, double-blinded, placebo-controlled, phase II clinical trial (NCT01836094) to evaluate the effects of oral USP MB (280 mg) on memory and cognition by using cerebral blood flow (CBF), evoked functional MRI (fMRI) and resting-state functional connectivity fMRI (fcMRI) on young (30 yo) healthy volunteers. Our findings suggest the MB has favorable cognitive and memory effects. The subjects, 28 subjects to date, did not experience any negative adverse event.
 
There are also a few MB clinical trials in mild to moderate AD and dementia (NCT01689246, NCT01689233, NCT01626378). An abstract of a phase II clinical trial reported that daily oral doses of 300 mg non-reduced form of MB (methylthioninium chloride), under trade name “Rember” (TauRx Therapeutics, Inc.), slowed the progression of AD compared to placebo. Ongoing phase III clinical trials use a proprietary reduced form of methylene blue (leukomethylene blue, LMTX™, TauRx) in mild and moderate AD and variant frontotemporal dementia. Our clinical trial differs from these clinical trials in several aspects: (1) TauRx phase II and phase III trials enrolled subjects with mild to severe Alzheimer’s disease and frontotemporal dementia (no MCI). Our study will be the first phase II clinical trial using MB in MCI, where early intervention is likely more effective. (2) TauRx phase II clinical trial used a large number of subjects with mild to moderate Alzheimer’s dementia and a larger dose up to 300 mg daily for one year with Rember™ (non-reduced form of MB). Our phase II trial will offer a markedly lower sample size, lower dose, and shorter duration, enabled by objective and powerful fMRI readouts. (3) The TauRx phase III clinical trial uses LMTX™, a new reduced form of MB that is less well studied. Our phase II trial will use the non-proprietary non-reduced form of MB (methylthioninium chloride), which has been used in most preclinical studies and clinical trials. (4) Subjects will be recruited from among well-characterized participants and a large cohort in the Texas Alzheimer’s Research and Care Consortium (TARCC). These subjects all have longitudinal psychometrics, and serum protein biomarkers on file, and frozen serum samples and DNA stored for future analyses. (4) The TauRx trials target to inhibit tau aggregation in neurofibrillary tangles of AD and demented patients, whereas we target to support healthy cognitive function by increasing mitochondrial oxidative energy metabolism and reducing oxidative stress in aging individuals before onset of AD neuropathology and dementia.
 
Our proposed phase II trial is very similar to our current phase II trial (NCT01836094) except it now includes middle aged, MCI and Alzheimer’s disease subjects and daily MB dose for 2 to 12 weeks (as opposed to healthy subjects and single dose) as well as additional neuropsychological tests.
 |
| 
Item 4
Purpose and rationale
Insert purpose, objectives and research questions/hypotheses here. If you cut and paste from another document, make sure the excerpted material answers the question
 | 
The purpose of the current IND proposal is to test the hypothesis whether daily oral MB for 2 to 12 weeks will improve memory, attention, cognition and functional connectivity in healthy middle aged, and healthy elderly as well as MCI and AD subjects by using objective MRI readouts and standard neuropsychological tests. subjects by using objective MRI readouts and standard neuropsychological tests. MRI readouts include evoked functional MRI (fMRI), cerebral blood flow (CBF), and resting-state functional connectivity fMRI (fcMRI). We will utilize a double-blinded, placebo-controlled phase II clinical trial.
 
MRI and neuropsychological tests will be administered over about 1.5 hours before oral MB, and again about 2 weeks after oral MB. The subject will have the option to continue for another 10 weeks after the completion of the first two weeks. The primary outcome measures will include fMRI readouts to assess episodic memory, working memory and sustained attention, respectively, before and two weeks after MB. Secondary outcome measures will include standard neuropsychological tests.
  |

|   |  |  |
|---|--|--|
| 
Item 5
Study Population(s) Being Recruited
 
In your recruitment plan, how many different populations of prospective subjects do you plan to target?
Provide number: 4
 | 
Identify the criteria for inclusion:
 | 
Identify the criteria for exclusion:
 |
|---|--|--|

|   |  |  |
|---|--|--|
| 
e.g., a population can be individuals with type 2 diabetes controlled with diet and/or a population of healthy controls. Or a population can be individuals attending an education program, etc.
 
List each different population on a separate row and provide a short descriptive label:
(e.g., normal-healthy, diabetics, parents, children, etc.)
 
To add rows use copy & paste
 |  |  |
| 
healthy middle aged
  | 
45 – 64 years old
All genders
All minorities
English, Spanish, or multilingual speakers
 | 
Pregnancy or breastfeeding, Contraindication for MRI, such as Claustrophobia and magnetic metal implants, Glucose-6-phosphate deficiency, methemoglobinemia, Anemia, Allergy to MB, Color-blindness, Craniotomy, craniectomy or endovascular neurosurgery, A current diagnosis of stroke, transient ischemic attack (TIA), any primary neurodegenerative disorder, or any other causes of neuropsychologic disturbances or secondary dementia (MCI or AD does not exclude subject), A serious intercurrent illness likely to cause death within the next 5 years, such as terminal cancer, Alcohol and/or drug abuse, Any detection of an unknown disease process (eg. new tumor) on the study's neuroimaging at the discretion of the investigators, A systolic blood pressure <math>\geq 180</math> mmHg and/or a diastolic blood pressure <math>\geq 105</math> mmHg, Severe difficulty or an inability to perform any one of the 6 Katz Activities of Daily Living, Patients who are unlikely to comply with trial visit schedule or with trial medication, On any psychiatric serotonergic antidepressant medication or psychotropic medication within the last 5 weeks, Diagnosis of epilepsy, traumatic brain injury with loss of consciousness, psychosis, panic attacks, Chronic kidney disease or Cirrhosis, Liver or renal transplants. Known hypersensitivity to thiazide diuretics and phenothiazines, Any other condition, which in the opinion of the investigator, would put the participant at risk and warrant exclusion from the study
 |
| 
healthy elderly
  | 
65 – 89 years old
All genders
All minorities
English, Spanish, or multilingual speakers
 | 
Pregnancy or breastfeeding, Contraindication for MRI, such as Claustrophobia and magnetic metal implants, Glucose-6-phosphate deficiency, methemoglobinemia, Anemia, Allergy to MB, Color-blindness, Craniotomy, craniectomy or endovascular neurosurgery, A current diagnosis of stroke, transient ischemic attack (TIA), any primary neurodegenerative disorder, or any other causes of neuropsychologic disturbances or secondary dementia (MCI or AD does not exclude subject), A serious intercurrent illness likely to cause death within the next 5 years, such as terminal cancer, Alcohol and/or drug abuse, Any detection of an unknown disease process (eg. new tumor) on the study's neuroimaging at the discretion of the investigators, A systolic blood
  |

|   |  |  |
|---|--|--|
|   |  | 
pressure <math>\geq 180</math> mmHg and/or a diastolic blood pressure <math>\geq 105</math> mmHg, Severe difficulty or an inability to perform any one of the 6 Katz Activities of Daily Living, Patients who are unlikely to comply with trial visit schedule or with trial medication, On any psychiatric serotonergic antidepressant medication or psychotropic medication within the last 5 weeks, Diagnosis of epilepsy, traumatic brain injury with loss of consciousness, psychosis, panic attacks, Chronic kidney disease or Cirrhosis, Liver or renal transplants. Known hypersensitivity to thiazide diuretics and phenothiazines, Any other condition, which in the opinion of the investigator, would put the participant at risk and warrant exclusion from the study
  |
| MCI   | 
45 – 89 years old
All genders
All minorities
English, Spanish, or multilingual speakers
 
Participants will meet the criteria for amnesic and non-amnesic (single or multiple domain) and mild AD such as those currently used by Texas Alzheimer's Research and Care Consortium (TARCC) consensus diagnosis. The AD subjects will only include early stage, late-onset, sporadic-type MB.
 | 
Pregnancy or breastfeeding, Contraindication for MRI, such as Claustrophobia and magnetic metal implants, Glucose-6-phosphate deficiency, methemoglobinemia, Anemia, Allergy to MB, Color-blindness, Craniotomy, craniectomy or endovascular neurosurgery, A current diagnosis of stroke, transient ischemic attack (TIA), any primary neurodegenerative disorder, or any other causes of neuropsychologic disturbances or secondary dementia (MCI or AD does not exclude subject), A serious intercurrent illness likely to cause death within the next 5 years, such as terminal cancer, Alcohol and/or drug abuse, Any detection of an unknown disease process (eg. new tumor) on the study's neuroimaging at the discretion of the investigators, A systolic blood pressure <math>\geq 180</math> mmHg and/or a diastolic blood pressure <math>\geq 105</math> mmHg, Severe difficulty or an inability to perform any one of the 6 Katz Activities of Daily Living, Patients who are unlikely to comply with trial visit schedule or with trial medication, On any psychiatric serotonergic antidepressant medication or psychotropic medication within the last 5 weeks, Diagnosis of epilepsy, traumatic brain injury with loss of consciousness, psychosis, panic attacks, Chronic kidney disease or Cirrhosis, Liver or renal transplants. Known hypersensitivity to thiazide diuretics and phenothiazines, Any other condition, which in the opinion of the investigator, would put the participant at risk and warrant exclusion from the study
 |
| AD (Alzheimer's Early-stage, late-onset, sporadic-type) | 
65 – 89 years old
All genders
All minorities
English, Spanish, or multilingual speakers
 
Participants will meet the criteria for amnesic and non-amnesic (single or multiple domain) and mild AD such as those currently used by Texas Alzheimer's Research and Care Consortium (TARCC) consensus diagnosis. The AD subjects will only include early stage, late-onset, sporadic-type MB.
 | 
Pregnancy or breastfeeding, Contraindication for MRI, such as Claustrophobia and magnetic metal implants, Glucose-6-phosphate deficiency, methemoglobinemia, Anemia, Allergy to MB, Color-blindness, Craniotomy, craniectomy or endovascular neurosurgery, A current diagnosis of stroke, transient ischemic attack (TIA), any primary neurodegenerative disorder, or any other causes of neuropsychologic disturbances or secondary dementia (MCI or AD does not exclude subject), A serious intercurrent illness likely to cause death within the next 5 years, such as terminal cancer, Alcohol and/or drug abuse, Any detection of an unknown disease process (eg. new tumor) on the study's neuroimaging at the
  |

|  |   |
|--|---|
|  | 
discretion of the investigators, A systolic blood pressure <math>\geq 180</math> mmHg and/or a diastolic blood pressure <math>\geq 105</math> mmHg, Severe difficulty or an inability to perform any one of the 6 Katz Activities of Daily Living, Patients who are unlikely to comply with trial visit schedule or with trial medication, On any psychiatric serotonergic antidepressant medication or psychotropic medication within the last 5 weeks, Diagnosis of epilepsy, traumatic brain injury with loss of consciousness, psychosis, panic attacks, Chronic kidney disease or Cirrhosis, Liver or renal transplants. Known hypersensitivity to thiazide diuretics and phenothiazines, Any other condition, which in the opinion of the investigator, would put the participant at risk and warrant exclusion from the study
 |
|--|---|

|  |   |
|--|---|
| 
Item 6
   |   |
| 
Research Plan / Description of the Research Methods a. Provide a comprehensive narrative describing the research methods. Provide the plan for data analysis (include as applicable the sample size calculation).
 |   |
|  | 
Step-by-Step Methods: 
 
Adult volunteers will be studied using a randomized, double-blinded, placebo-controlled design. Placebo arms will be included for healthy middle aged, healthy elderly, MCI and AD groups as controls. USP Methylene blue (MB) and placebo pills will be compounded into blue immediate release capsules. The subject will take 3 pills of MB or placebo (94mg per pill) three times a day with each meal. Placebo will be FD&C Blue # 2 which is a powder similar to the powder form of methylene blue. Each arm will also receive a pill of phenazopyridine hydrochloride (97.5 mg, marketed as Azo Standard) with each daily dosage. Phenazopyridine is a safe OTC product used for urinary discomfort that turns urine brownish. This drug will be given to both MB and placebo groups so that both show similar urine discoloration. This choice of administration is justified not only to maintain the blind procedure but because it would prevent any mild discomfort experienced by MB urinary excretion during chronic treatment. The subject, person administering the drug, and data analysts will not know whether the intervention is placebo or MB. The design will only be unblinded at the last steps when necessary. All subjects will be told that the pill they take may or may not cause urine/feces discoloration depending on individual's metabolism.
 
Step by Step:
The healthy elderly, MCI and AD subjects will be recruited from the Texas Alzheimer's Research and Care Consortium (TARCC). A neuropsychological battery of tests (eg. logical memory I, logical memory II, verbal fluency/COWA, Instrumental Activities of Daily Living (IADL), Global Depressive Scale (GDS), etc.) will be administered for all subjects before MRI study (2 month window).
 
Baseline MRI scan will be performed during visit 1.
 
Subject will be given labeled pill organizers with pills to take on days 1 through 14. Subject will be contacted via telephone on days 3, 7 and 11 (<math>\pm 2</math> days) to document any adverse event or problem. After 2 weeks <math>\pm 3</math> days of MB (282 mg, oral x 14 days) or placebo, another neuropsychological tests and MRI scan will be obtained. On visit 2, the subject will be given the option to continue for another 10 weeks. During visit 3, after 10 weeks <math>\pm 3</math> days, the subject will complete the subset of neuropsychological tests completed in visit 1, and some of the MRI scans completed in visit 1.
 
For MRI, task-evoked BOLD fMRI, cerebral blood flow (CBF), resting-state fMRI, and CBF will be performed. For the task-evoked BOLD fMRI, subjects will perform the following scans while in the
 |

scanner:

Delayed match-to-sample memory task: The DMS task measures reaction time in terms of memory retrieval latency. The subject views a 6x6 pattern for 4 seconds. After six seconds, the subject is presented with two patterns and the subject presses the left or right button based on whether the picture on the left or the right is the same as the previous picture. The correct and incorrect answers are recorded. This exercise is repeated with 22 random patterns for approximately 10 mins.

Face-Name Task: The subject is shown blocks of stimuli where a novel or familiar face is paired with a name. In a later run, the subjects are asked whether the correct name is matched with the correct face. The correct and incorrect answers are recorded. The acquisition of data is divided into encoding and recognition tasks. This exercise is repeated many times lasting about 10 minutes.

Psychomotor vigilance task: The PVT measures attention and time-on-task effects. The subject receives a visual cue that alerts them to press a button as fast as possible. The reaction time is recorded. A rest period follows for 4-8 seconds. This exercise is repeated 30 times, lasting about 7-10 minutes.

Subject behavioral data (ie. Correct responses, reaction time) will be recorded simultaneously while the MRI data is acquired by a computer.

For CBF, the subject is instructed to close his or her eyes and relax in the scanner without falling asleep for 5-10 minutes.

For resting-state fMRI, the subject is told to close eyes and not to think about a particular topic, lasting about 10 minutes.

In addition, CBF will be measured during inhalation of medical-grade 5% CO2 in air for 3-5 minutes for calibration on all three visits. Standard anatomical MRI will also be acquired for co-registration. Diffusion tensor imaging (DTI) (5-7minutes) will also be acquired at one of the three visits.

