#### Intervention Groups:

| Arms                                 | Assigned Interventions  |
|--------------------------------------|---|
| Experimental:
Healthy Middle Aged | Drug: Methylene Blue (USP grade, 282 mg oral, up to 12 weeks)
Phenazopyridine hydrochloride (97.5 mg oral, up to 12 weeks)             |
| Placebo: Healthy Middle Aged         | Drug: FD&C Blue # 2 (USP grade, 282 mg oral, up to 12 weeks)
Phenazopyridine hydrochloride (97.5 mg oral, up to 2 weeks)               |
| Experimental:
Healthy Elderly MB  | Drug: Methylene Blue (USP grade, 282 mg oral, once daily, up to 12 weeks)
Phenazopyridine hydrochloride (97.5 mg oral, up to 12 weeks) |
| Placebo: Healthy Elderly MB          | Drug: FD&C Blue # 2 (USP grade, 282 mg oral, up to 12 weeks)
Phenazopyridine hydrochloride (97.5 mg oral, up to 12 weeks)              |
| Experimental:
MCI MB              | Drug: Methylene Blue (USP grade, 282 mg oral, once daily, up to 12 weeks)
Phenazopyridine hydrochloride (97.5 mg oral, up to 12 weeks) |
| Placebo:
MCI MB                   | Drug: FD&C Blue # 2 (USP grade, 282 mg oral, up to 12 weeks)
Phenazopyridine hydrochloride (97.5 mg oral, up to 12 weeks)              |
| Experimental:
AD MB               | Drug: Methylene Blue (USP grade, 282 mg oral, up to 12 weeks)
Phenazopyridine hydrochloride (97.5 mg oral, up to 12 weeks)             |

Placebo:  
AD MB

Drug: FD&C Blue # 2 (USP grade, 282 mg oral, up to 12 weeks)  
Phenazopyridine hydrochloride (97.5 mg oral, up to 12 weeks)

**The daily 282mg of MB or place will be divided into three doses of 94mg each to minimize the risk for urinary irritation. A second pill of Azo will be taken during one of these doses.**

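### Three slips in the dosing text need correcting: one sentence literally gives 846 mg a day instead of 282 mg, two arm rows say once daily, and one placebo row stops the urine-masking pill at 2 weeks

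*Combined protocol and SAP*

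**What the plan says.** The dose is described in four places.

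- **Item 2, abstract, Methods:** a daily dose of 282 mg, with the schedule "Subjects will take 3 pills of MB/placebo each day (1 with each meal (94mg of MB per pill".
- **Item 6, Step-by-Step Methods:** "The subject will take 3 pills of MB or placebo (94mg per pill) three times a day with each meal". Later in the same item the regimen is "days of MB (282 mg, oral x 14 days) or placebo".
- **Item 6, Intervention Groups table:** all eight arm rows give 282 mg. Two of them, the experimental healthy elderly and experimental MCI rows, read "Drug: Methylene Blue (USP grade, 282 mg oral, once daily, up to 12 weeks". The other six do not state a frequency.
- **Note under that table:** for MB and placebo alike, the daily amount "will be divided into three doses of 94mg each to minimize the risk for urinary irritation". It adds "A second pill of Azo will be taken during one of these doses".

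On the urine-masking pill, Step-by-Step Methods sets a rule for all arms: "Each arm will also receive a pill of phenazopyridine hydrochloride (97.5 mg, marketed as Azo Standard) with each daily dosage". The reason given is that urine should look alike in both groups and the blind be kept. In the arm table, phenazopyridine runs for up to 12 weeks in seven rows. The placebo healthy middle aged row says "Phenazopyridine hydrochloride (97.5 mg oral, up to 2 weeks", while its placebo capsule runs for up to 12 weeks.

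**The concern.** These are the instructions from which capsules are dispensed and the blind is maintained, and each contradicts the rest of the document.

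- **Dose sentence.** It puts three pills before three occasions a day. Anyone filling organisers from that sentence alone could give three times the intended dose. This is the only slip that changes the daily total.
- **Once daily.** Followed as written, subjects in those two rows would take 282 mg on one occasion instead of 94 mg on three, which works against the stated reason for dividing the dose. Only MB rows carry the wording, so the MB and placebo schedules would also differ within two populations of a double-blind trial.
- **Masking pill.** Followed as written, healthy middle-aged placebo subjects who take the optional extension would lose the masking pill after week 2 while their MB counterparts keep it. The Outcomes section lists 12 weeks as a time point for every primary outcome. These include task performance and the neuropsychological battery, which a subject's guess about allocation could influence.

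**Working it through.** **Inputs.** Capsule strength 94 mg (Item 2; Item 6). Stated daily dose 282 mg (Item 2; all eight arm rows). Initial treatment 14 days, optional extension 10 weeks (Item 6). Phenazopyridine one pill a day (Item 2).

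**1. The plan's own figure.** One capsule × 3 meals × 94 mg = 282 mg a day. This reproduces the stated dose exactly.

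**2. The Step-by-Step sentence read literally.**
- Daily dose: 3 capsules × 3 occasions × 94 mg = 846 mg.
- Ratio: 846 / 282 = 3.
- Capsules over 14 days: 9 × 14 = 126, against 3 × 14 = 42.

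For scale, Item 3 refers to 4 mg/kg daily as having been used safely. The documents give no body weight. Assuming 60 to 90 kg:

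| Assumed weight | 282 mg/day | 846 mg/day |
|---|---|---|
| 60 kg | 4.7 mg/kg | 14.1 mg/kg |
| 90 kg | 3.1 mg/kg | 9.4 mg/kg |

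**3. Once-daily wording, counted by row.** It appears in 2 of 4 MB rows and 0 of 4 placebo rows, so 2 of 8 in all. The amount per occasion would be 282 mg instead of 94 mg. The daily total stays at 282 mg.

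**4. Masking pill, counted by row.** Up to 12 weeks in 7 of 8 rows; up to 2 weeks in 1 of 8.
- Gap: 12 − 2 = 10 weeks.
- Pills missed: 10 × 7 × 1 = 70 at most per extending subject in that arm.
- Gap within the first 2 weeks: 0 days.

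The number of subjects who will extend is not given, so the total affected cannot be computed.

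**The case against.** The strongest reply is that the intended regimen can be recovered in every case. The Step-by-Step sentence can be read as three pills in total, spread over the meals. The figure 846 mg appears nowhere in the documents, and every explicit statement of the daily total is 282 mg. Subjects receive labelled organisers, so they do not work out the dose from this sentence, and the pharmacy instructions are not in the documents. The note under the table applies to all arms and overrides the once-daily wording. The general phenazopyridine rule and the seven other rows contradict the odd one. Subjects are also told that discoloration may or may not occur, which partly protects the blind.

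Most of this stands, and it limits the point to wording errors rather than a flawed design. Three further limits are fair. The remark about a second Azo pill is ambiguous: it may mean Azo as the second pill at that meal, or a second Azo pill. It is therefore weak support for one capsule per dose, though the abstract and the rest of the note are enough. An undivided dose would weaken the protection against urinary irritation rather than remove it, since phenazopyridine is also given as a urinary analgesic. And Item 4 describes the primary measures as before and two weeks after treatment, a comparison that the masking-pill row leaves untouched.

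What does not follow is that the text can be left alone. A dosing sentence with a threefold reading should not depend on staff checking it against other sections.

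**Conclusion.** The concern holds on all three parts, as wording errors in operative instructions that should be fixed.

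- The dose sentence, read literally, gives three times the intended daily dose. This rests on that reading being followed over the other dose statements.
- The once-daily wording affects 2 of 8 rows and leaves the daily total unchanged.
- The masking gap affects 1 of 8 rows. It is confined to weeks 3 to 12 and to healthy middle-aged placebo subjects who extend, and it matters for the 12-week time point in that population only.

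Nothing in the documents shows that anyone was misdosed or unblinded. No sample size, error rate or analysis is altered. The mg/kg comparison depends on an assumed weight range and the conclusion does not need it.

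**What to change.** 1. **Step-by-Step Methods:** replace the sentence with wording such as: one 94 mg capsule of MB or placebo with each of three meals (3 capsules, 282 mg per day).
2. **Intervention Groups table:** delete the once-daily wording from the experimental healthy elderly and experimental MCI rows.
3. **Intervention Groups table:** in the placebo healthy middle aged row, change the phenazopyridine duration from 2 to 12 weeks.
4. **Dispensing materials:** check pharmacy labels and pill organisers against the corrected text.

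The cost is three small wording edits and one check of labels and organisers. No subjects, procedures or analyses are added.

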**OUTCOMES:**

**Primary Outcome Measures:**

Working memory task fMRI measures

[Time Frame: baseline, 2 weeks ± 3 days, 12 weeks ± 3 days]

Delayed Match to Sample Task behavioral (ie. correct number of responses) and fMRI measures will be acquired simultaneously

Episodic memory task fMRI measures

[Time Frame: baseline, 2 weeks ± 3 days, 12 weeks ± 3 days]

Face-Name Task behavioral (ie. correct recalls) and fMRI measures will be acquired simultaneously

Sustained attention task fMRI measures

[Time Frame: baseline, 2 weeks ± 3 days, 12 weeks ± 3 days]

Psychomotor vigilance task behavioral (ie. reaction time) and fMRI measures will be acquired simultaneously

Neuropsychological Battery

[Time Frame: baseline, 2 weeks ± 3 days, 12 weeks ± 3 days]

TARCC designed psychometric tests

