**Tertiary Outcome Measures:**

Functional Connectivity (resting state) fMRI measures

[Time Frame: baseline, 2 weeks ± 3 days, 12 weeks ± 15 days]

fMRI measurements will be obtained while the subject rests in the scanner

CO2 challenge: Cerebral blood flow measurements will be acquired during a brief (3-5 minutes) inhalation of medical-grade 5% CO2 in air for fMRI signal calibration purposes.

[Time Frame: baseline, 2 weeks ± 3 days, 12 weeks ± 15 days ]

Data Analysis Plan: Statistical parametric analysis will be performed to generate activation maps using established fMRI software. Task-evoked changes in brain activities will be analyzed and contrasted between placebo and MB conditions. ANOVAs, paired t and 2-sample t-tests will be used in analyzing the reaction times and success/failure rates in the DMS, FNT and PVT, with blocks (pre-MB vs. post-MB) as a within-subject variable and treatment (MB vs. Placebo) as a between-subject variable. Paired t-test will be used for group comparison with  $p < 0.05$  (False Discovery Rate  $q < 0.05$ ) considered statistically significant.

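### The scheduled adverse-event calls stop with the initial 14-day period; none is named for the optional 10-week extension on the same daily dose

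*Combined protocol and SAP*

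**What the plan says.** Item 6 (Step by Step) describes dispensing pills for days 1 to 14 and then sets the calls: "Subject will be contacted via telephone on days 3, 7 and 11", within 2 days either way. Their purpose is "to document any adverse event or problem".

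At visit 2, about two weeks after the start, "another neuropsychological tests and MRI scan will be obtained". Item 2 adds that after this visit "the subject will be given the option to continue the study for another 10 weeks". The Intervention Groups table gives 282 mg of methylene blue (MB), or the matching dye, for up to 12 weeks in all four populations.

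At visit 3, "the subject will complete the subset of neuropsychological tests completed in visit 1, and some of the MRI scans completed in visit 1".

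Neither visit description mentions asking about adverse events. The primary, secondary and tertiary outcome lists contain no safety measure. Item 7 (Risks Section) refers risks to the consent document.

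**The concern.** The protocol sets its own standard in the first two weeks: an active inquiry about every four days. The extension is five times as long (70 days against 14) on the same daily regimen, yet the call schedule was not carried into it and no reason is given. A team that follows the stated schedule would make no adverse-event call during those ten weeks.

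What is at stake is participant safety. An event that begins in the extension could be found late, or not recorded, while daily dosing goes on. The subjects are up to 89 years old and include people with mild cognitive impairment (MCI) and Alzheimer's disease (AD). The team's own event-free experience, as Item 3 describes it, comes from single doses in 28 young healthy volunteers, so it does not bear on repeated dosing in these groups.

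**Working it through.** The plan states no figure to reproduce. The check is day arithmetic plus a reading of the whole supplied text for adverse-event, safety or telephone contacts.

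**Inputs**
- Calls on days 3, 7 and 11, each ±2 days (Item 6, Step by Step).
- Visit 2 at 2 weeks ± 3 days, and visit 3 at 10 weeks ± 3 days after the option to continue (same place).
- Visit timing in the Primary Outcome Measures: "Time Frame: baseline, 2 weeks ± 3 days, 12 weeks ± 3 days".
- Total dosing of up to 12 weeks (Item 4 and the Intervention Groups table). I read this as 2 + 10 weeks.

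**Where the calls fall**
- Windows: days 1–5, 5–9 and 9–13. All lie within days 1–14.
- Calls named from day 15 to day 84: 0.

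**Interval for a continuer**
- Visit 2 is nominally 2 × 7 = day 14, and visit 3 is 12 × 7 = day 84.
- Visit 2 to visit 3: 84 − 14 = 70 days.
- Under the Item 6 window, counted from visit 2: 70 ± 3 = 67 to 73 days.
- Under the primary-outcome windows, both counted from baseline (visit 2 on days 11–17, visit 3 on days 81–87): 81 − 17 = 64 to 87 − 11 = 76 days.

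**Non-continuers**
- Last call to visit 2: 14 − 11 = 3 days. They are little affected.

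**After the change, with the question also asked on days 14 and 84**
- Calls at weeks 6 and 10 (days 42 and 70): 42 − 14 = 28, 70 − 42 = 28, 84 − 70 = 14. The longest interval is 28 days.
- Calls at weeks 4, 6, 8 and 10 (days 28, 42, 56 and 70): every interval is 14 days.

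**Search of the text**
- Apart from the Item 6 calls, adverse events are mentioned only in Item 3, about the single-dose trial.

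**The case against.** The strongest reply is that the file is incomplete. It is an institutional review form. Item 7 points to the consent document and to an institutional form, neither of which was available, and the text ends within that item. A safety-monitoring plan could sit in either. Item 6 is also brief about the extension: it does not say how pills for weeks 3 to 12 are dispensed, so it is clearly not a full list of extension contacts. This stands as a limit. The finding is that no call is named in the supplied text. A reader might infer that the investigators chose to stop monitoring, and the documents do not support that. Still, Item 7 refers risks to the consent document, not a contact schedule, and Item 6 is where the existing calls were written down.

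Several features also lower the expected consequence:
- Continuation is chosen in person at visit 2, after two weeks on the same dose and three calls.
- Visits 2 and 3 are face-to-face chances to report.
- Azo is given partly because "it would prevent any mild discomfort experienced by MB urinary excretion during chronic treatment", and the dose is divided into three.
- Anemia, methemoglobinemia and other risk conditions are excluded.
- Item 3 cites safe daily use for one year.

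All of this is fair. It makes closer contact early on a reasonable plan, but it does not record events that occur later.

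Three stronger readings should be resisted. First, 70 of 84 dosing days without a call does not mean 70 unobserved days, because an inquiry asks about the days before it. Second, the text gives no evidence that MCI or early AD subjects under-report, and those with severe difficulty in basic daily activities are excluded. Third, nothing suggests a distorted treatment comparison: both arms share the schedule, and no listed efficacy outcome depends on the calls.

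**Conclusion.** The point holds as a participant-safety gap in the stated schedule. For subjects who continue, there is nominally a 70-day interval between visits 2 and 3 (67 to 73 days under the Item 6 window) with no scheduled adverse-event contact in the supplied text.

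The size rests on two assumptions: that the extension brings total dosing to 12 weeks, and that no unseen form supplies the missing contacts. The second cannot be checked here. The number of events missed cannot be estimated. It is a change worth making because it is cheap and the protocol already uses the procedure. It does not threaten the trial's efficacy conclusions.

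**What to change.** In Item 6 (Step by Step), continue the existing call through the extension at a fixed interval that the sponsor chooses, for example every 4 weeks (weeks 6 and 10) or every 2 weeks (weeks 4, 6, 8 and 10). State that the same adverse-event question is asked at visits 2 and 3. If a separate monitoring plan already provides this, cite it in Item 6 instead.

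The cost is two to four short calls per continuing subject, one added question at two existing visits, and a few lines of protocol text. No new kind of procedure is needed. The documents do not describe staffing, so caller time is not costed.
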